We propose a single arm trial of TB preventive therapy to assess its toxicity, measure adherence, and determine whether its benefits outweigh its risks when given to TB/HIV-infected drinkers (n=200). We will provide 6 months of INH to HIV/TB infected drinkers (n=200) and non-drinkers (n=100) to describe safety, tolerability, and adherence among drinkers and by level of drinking. We will conduct frequent monitoring for toxicity, and assess toxicity as well as adherence. We will evaluate the safety, tolerability and adherence by level of drinking, measured by self-report and augmented by phosphatidylethanol (PEth), an established biomarker for alcohol consumption. We will employ objective measures of adherence, including electronic medication monitoring (EMM) of pill bottle opening, pharmacy pill counts, and a novel measure of INH exposure, that is, INH concentration in hair. We will actively monitor for toxicity, using the U.S. standard of care for laboratory monitoring during TB preventive therapy for heavy drinkers. We will use the safety, tolerability, and adherence results, together with the known efficacy and mortality benefit of TB preventive therapy in HIV-infected persons in SSA, and our established decision analytic model of TB preventive therapy, to determine whether the mortality and quality of life benefits of TB preventive therapy outweigh the toxicity risks for HIV-infected drinkers in resource limited settings.

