C.3.4 Enrollment – Eligibility screening and baseline study activities. Participants will initially be recruited from the Uganda ARCH cohorts, in which participants have given permission for re-contact for further study. Of the 465 current drinkers recruited in these cohorts, we estimate that we will be able to contact 75% (N=349), and that 60% of those will meet eligibility criteria (n=209). The remaining participants will be recruited from persons reporting any alcohol use on the AUDIT, approximately 25% of clinic patients,¹⁰⁹ which is routinely administered at initial ISS Clinic visit. We will also recruit patients who report no prior year alcohol use for the abstainer group. We will review the EMR for potential participants and those that meet preliminary study eligibility (i.e. age, on ART for 6 months) will be invited to meet with a research assistant to determine further eligibility. If further eligibility is established, the research assistant, a licensed clinical officer, will seek informed consent for further screening to rule out active TB, existing liver disease, and to assess TST status (Figure 1). A blood draw for ALT/AST testing will be performed, a TST will be placed, and if the participant reports symptoms of possible active TB (cough >24 hours, fever, weight loss, night sweats), further tests (chest X-ray and sputum collection for acid fast bacilli [AFB] stain and Xpert MTB/RIF assay) will be conducted. Those with abnormal chest X-ray results or a positive AFB or Xpert test will be brought to the MRRH TB clinic per hospital protocol. Patients will be asked to return in 2 days for TST reading, informed consent will be requested if active TB has been ruled out and TST is positive. After informed consent is obtained, the baseline visit will include study questionnaire completion, blood draw, and medication dispensing.

Aim 1: To examine the safety and tolerability of 6H for HIV-infected drinkers, measured by hepatotoxicity. Our main aim is to estimate safety overall among drinkers (primary) and by level of drinking (secondary). We will additionally compare safety and tolerability by level of drinking in secondary analyses.

Aim 2: To estimate the level of adherence to TB preventive therapy, overall among drinkers (primary), by month on therapy. Secondarily, we will estimate adherence by drinking level and compare adherence levels across drinking levels. We hypothesize that adherence will be highest among non-drinkers.

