Alcohol consumption. Heavy drinking will be defined as either PEth \geq 50 ng/mL or AUDIT-C positive (\geq 3 for women, \geq 4 for men). The AUDIT-C will be modified to cover the prior 3 months. By combining two highly specific measures, we will increase the sensitivity for detecting heavy alcohol use over using each measure alone, as in our previous analyses of heavy alcohol use by persons with HIV in Uganda.^{81,82}

We will collect self-reported measures of alcohol use at baseline using the AUDIT-C and the CAGE,¹²⁰ which are readily available for use in clinical practice. For analyses that examine level of drinking, we will categorize

the scores as low risk drinking, (women: AUDIT-C 0-2; men: AUDIT-C 0-3), heavy drinking (women: AUDIT-C 3-5; men: AUDIT-C 4-5), and very high risk drinking (AUDIT-C ≥ 8).¹²¹ The corresponding cutoffs for the CAGE will be scores of 0, 1, and 2-4.¹²² We will additionally measure alcohol consumption using tools that are not dependent on standardized drink volume or concentration, e.g. money spent drinking, level of intoxication, and PEth level, as in our previous studies.¹⁰¹

Covariates. Covariates measured at baseline will include gender, age, body mass index (BMI), CD4 cell count, HIV viral load, ALT/AST, active hepatitis B viral infection (HBsAg), symptoms of depression,¹²³ smoking, nicotine dependence,¹²⁴ and duration on ART – also recently added on baseline platelet count, FIB-4 score, and eGFR. Covariates measured at baseline and follow-up will include current ART regimen, and the VAS and SRSI for self-reported ART adherence.

Table 3. Schedule of study visits and activities.

	Eligibility	Baseline	Week 2	Month 1	Month 2	Month 3	Month 4	Month 5	Month 6	Month 7	Follow-up
Initial eligibility determined, ALT/AST and TST testing. Chest X-ray and sputum collected if symptoms of active TB are reported.	X										
Enrollment/ baseline: Study interview, blood draw, medication dispensing		X									
Toxicity assessment (side effects and ALT/AST testing)			X	X	X	X	X	X	X	X	
Medication refill, pharmacy pill count, and EMM data download, and brief alcohol and adherence assessments			X	X	X	X	X	X	X		
Hair collection for INH concentration						X			X		
Follow-up: Study interview, blood draw, and screening for active TB						X			X		X

C.3.9 Statistical analyses for Aim 1.

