Primary analysis: Safety. The focus of this aim is the evaluation of safety among drinkers overall (primary) and by drinking levels (secondary). Thus the primary analysis set will be all participants who receive at least one dose of TB preventive therapy who are current drinkers. We will report the incidence of Grade 3/4 hepatotoxicity at any time during prescribed treatment along with 95% exact binomial confidence intervals (CIs).

Secondary analyses: Safety and tolerability will be estimated by level of alcohol use at baseline and during treatment. To examine safety and tolerability by alcohol consumption prior to treatment, we will report hepatotoxicity and treatment discontinuation stratified by level of drinking (heavy alcohol consumption, current but not heavy drinking, no drinking) at baseline. Fisher's exact test and exact logistic regression models adjusting for gender, hepatitis B co-infection, Cd4 cell count and/or viral suppression will be used to compare safety outcomes across drinking levels. To inform clinical practice, we will also report the outcomes by self-reported alcohol consumption levels using the AUDIT-C and the CAGE. We will also examine toxicity by level of PEth, using recently suggested PEth cutoffs. We will use generalized estimating equation logistic regression models to examine whether drinking level during the treatment period impacts safety and tolerability outcomes.

Secondary analysis: Comparison of hepatotoxicity rates to previous studies. We will also compare estimates and 95% CIs to those reported in published studies of TB preventive therapy in those with HIV, which found hepatotoxicity rates of 0.3-5.5%.

Sample size justification. We anticipate a total of 200 drinkers will be enrolled into the current study. Based on the Uganda ARCH cohort retention, we expect 90% 6-month study visit retention resulting in N=180 evaluable participants. We expect that the proportion of participants with any Grade 3/4 hepatotoxicity within the treatment period will be approximately at the midpoint of the range of toxicity rates published previously, i.e. 2.6%. Given this, we would expect approximately 5 safety events, and the length of a 95% exact binomial CI around the estimate would be 5.5%, (i.e. 0.9% to 6.4%).

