To illustrate power for secondary analyses, we also calculate the minimum detectable difference to compare safety between alcohol groups. I.e., to compare toxicity between any group of drinkers (either heavy drinkers or moderate drinkers, each expected to be approximately 1/3 of the sample) to non-drinkers (1/3 of the sample), we will have 80% power to detect a difference in toxicity rate of 0.095 or greater if the toxicity rate in the lighter drinkers/abstainers is 1% and alpha is set to 0.05 based on a Fisher's Exact test.

C.3.10 Statistical analyses for Aim 2.

Primary analysis: The goal of this aim is to estimate the level of adherence overall among drinkers and by drinking level (including abstainers). The analysis will consist of all participants enrolled. For those who are advised to discontinue therapy by the study physicians, adherence up until discontinuation will be used; however, additional sensitivity analyses will be conducted using alternative imputation strategies (e.g. using the midpoint between best and worst weeks, and assuming the worst case scenario of zero for the discontinued time period). We will report the percent adherence using EMM data over the treatment duration and 95% CIs overall among drinkers and by drinking level (heavy, non-heavy, abstainer), and fit multiple linear regression models, controlling for gender, to compare adherence across drinking categories. If the data are skewed, transformations will be performed (e.g., log transformation) or median regression if no appropriate transformation is identified.

Secondary analyses: Alternate measures of adherence and adherence over time and by level of alcohol use. Secondary measures of adherence will be analyzed using the same approach as described above. We will additionally conduct all adherence analyses excluding the first 40 days to remove a possible Hawthorne effect that may occur when patients are aware they are being monitored, but that often abates after one month. We will also conduct repeated measures analyses of monthly adherence data using linear mixed effects regression models, with month on treatment included as a predictor, to test the hypothesis that adherence changes over time. We will additionally use these analyses to assess whether drinking level at baseline and during treatment (using time-updated covariates) impact adherence.

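### The secondary comparison of adherence across drinking levels adjusts only for gender, leaving it open to confounding by factors already measured at baseline, such as age and duration on ART

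*Combined protocol and SAP*

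**What the plan says.** C.3.10 (paragraph labelled Primary analysis) defines the population, the outcome and the model for Aim 2:

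- Population: "The analysis will consist of all participants enrolled". The target is 200 drinkers and 100 non-drinkers.
- Outcome and estimates: "We will report the percent adherence using EMM data over the treatment duration and 95% CIs overall among drinkers and by drinking level".
- Comparison: "fit multiple linear regression models, controlling for gender, to compare adherence across drinking categories". A transformation or median regression is allowed if the data are skewed.

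The secondary adherence measures in C.3.10 are to be handled in the same way, and the hair isoniazid comparison (Secondary analyses, just before C.3.11) refers back to the adherence method. The repeated-measures models in C.3.10 name month and drinking level, and no confounders.

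The Specific Aims and the aims restated in C.3.4 rank adherence overall among drinkers as primary. Estimates by level and comparisons between levels are secondary. The comparison carries a directional hypothesis: "We hypothesize that adherence will be highest among non-drinkers".

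C.3.8 lists what is collected: "Covariates measured at baseline will include gender, age, body mass index (BMI), CD4 cell count, HIV viral load", followed by ALT/AST, hepatitis B status, depressive symptoms, smoking, nicotine dependence, duration on ART and some later additions. Also: "Covariates measured at baseline and follow-up will include current ART regimen, and the VAS and SRSI for self-reported ART adherence".

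For the Aim 1 comparison across drinking levels, C.3.9 plans "exact logistic regression models adjusting for gender, hepatitis B co-infection, Cd4 cell count and/or viral suppression".

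**The concern.** People who drink heavily, drink lightly or abstain may differ in more than gender. If the groups also differ in age or in time on ART, and either is related to taking a daily pill, the regression coefficient for drinking level mixes that difference with any association due to drinking. Adjustment for gender alone removes only the part that runs through gender.

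At stake is the interpretation of the hypothesis that non-drinkers adhere best. A difference could appear, or a real one be masked, because of a factor that the study has measured and left out of the model. Because the other adherence measures and hair isoniazid inherit the same model, their agreement with the EMM result would not be independent reassurance on this point.

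**Working it through.** **1. Is drinking level randomised?** No. The Study Design Overview and C.3.1 describe one arm. The remaining mentions of randomisation (C.3.7) and of two arms (C.3.12) do not make drinking level an assigned factor.

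**2. Is a wider adjustment planned elsewhere?** C.3.11 has an exploratory lasso for predictors of toxicity and adherence. It is a selection method: it can shrink a confounder to zero and gives no standard confidence interval for the drinking contrast. Its listed predictors name neither duration on ART nor depressive symptoms, although demographics would cover age. No section plans an adjusted sensitivity analysis for the contrast.

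**3. Do the documents point to a candidate confounder?** C.2 reports that heavy drinking rose after ART start in the first year of HIV care (per-month adjusted odds ratio 1.11). Section B says completion of preventive therapy was highest among people on ART and suggests that an existing pill routine may help. This makes duration on ART plausible, no more: everyone here is on ART, and neither statement measures the association in this population.

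**4. Is there a plan figure to reproduce?** C.3.10 gives no SD, power or detectable difference for adherence. The only between-level figure is for toxicity in C.3.9: 80% power for a difference of 0.095 over a 1% rate. Exact two-sided Fisher power for 1% against 10.5% is 80.7% with 100 per group (74.2% with 90). The stated figure thus corresponds to 100 per group, which is used below.

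**5. Precision of an adherence contrast, in SD units.**

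- SE = √(2/100) = 0.141 SD.
- Detectable difference at 80% power, two-sided 5%: (1.96 + 0.84) × 0.141 = 0.40 SD. With 90 per group (90% retention) it is 0.42 SD.

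**6. Illustration of bias. All inputs here are assumptions.** For one omitted binary confounder, bias = (its effect on adherence, in SD) × (its prevalence gap between two drinking groups), both after gender adjustment. With no true difference, the rejection probability is Φ(bias/SE − 1.96) + Φ(−bias/SE − 1.96).

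| Effect (SD) | Prevalence gap | Bias (SD) | Rejection under no true difference |
|---|---|---|---|
| 0.2 | 10 points | 0.02 | 5.2% |
| 0.3 | 20 points | 0.06 | 7.1% |
| 0.3 | 30 points | 0.09 | 9.8% |
| 0.5 | 40 points | 0.20 | 29.3% |

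On a percentage scale with an assumed SD of 20 points, SE = 20 × 0.141 = 2.83 points. An 8-point effect with a 15-point gap gives 0.15 × 8 = 1.2 points, or 0.42 SE, and a rejection rate of about 7%.

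**7. Cost of two more covariates.** The present model has an intercept, two drinking terms and gender, so residual df = 300 − 4 = 296. Adding age and duration on ART as linear terms leaves 294. If both explain nothing and are unrelated to drinking level, the SE rises by √(296/294) = 1.003, or 0.3%. With 270 participants it is √(266/264) = 1.004. Correlation with drinking level would raise this.

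**The case against.** The strongest reply has four parts.

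*The comparison is secondary and the hypothesis is associational.* This stands. The C.3.10 label could lead a reader to infer that the main Aim 2 result is at risk. It is not: overall adherence among drinkers and the level-specific estimates are descriptive and need no adjustment.

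*Confounding is not shown.* This also stands. A reader might infer that the comparison is confounded, or take a false-positive rate of 6% to 19% as a finding. That range corresponds to biases of 1 to 3 points at an assumed SD of 20. No section reports the association of any covariate with both drinking level and isoniazid adherence, and the modest 1.2-point example gives only about 7%.

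*Aim 3 does not use this contrast.* Correct. One might infer that a confounded difference would feed the decision model. C.4.2 stratifies therapy parameters by drinking level and takes adherence from observed refill, self-report and EMM data. The strata are current, heavy and very heavy drinking by AUDIT-C, and C.4.4 simulates drinkers only. Observed adherence within strata is the right input there.

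*Adjustment can do harm.* Partly right. Drinking may cause depressive symptoms or poor ART adherence, and adjusting for these could remove part of the association of interest. That argues for a small set, not for gender alone.

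The contrast with Aim 1 should not be pressed either. C.3.9 names more covariates for a model with about 5 expected events among drinkers, which may say more about that model than about this one. It shows only that sample size is no reason to stop at gender here.

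**Conclusion.** The point holds for the between-level contrasts in EMM adherence, the secondary adherence measures and hair isoniazid. They compare non-randomised groups with gender as the only adjuster, without a stated reason, while age and duration on ART are already collected. The lasso in C.3.11 does not fill the gap.

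The contrasts are open to confounding; whether they are confounded, in which direction and by how much, cannot be derived from the documents. The 5.2% to 29% range in the table rests on assumed effects and prevalence gaps, three equal groups of 100 and a normal approximation. Several confounders acting in the same direction would add up; in opposite directions they would offset each other. Equal groups are themselves uncertain: the 73% heavy share in Table 2 would give 146 heavy and 54 non-heavy among 200 drinkers, with detectable differences against 100 non-drinkers of 0.36 and 0.47 SD.

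This is an inexpensive improvement to a secondary analysis. It does not undermine the primary Aim 2 estimate, the descriptive results by drinking level or Aim 3.

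**What to change.** In C.3.10, prespecify gender, age and baseline duration on ART as the adjustment set for the drinking-level contrasts, with one sentence of rationale. State that the same set applies to the secondary adherence measures and to hair isoniazid, and to median regression if that replaces the linear model. Report the gender-only model beside it, so that readers can see what the adjustment changes.

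Add depressive symptoms and baseline self-reported ART adherence only in a labelled sensitivity model, and say that they may lie on the path from drinking to adherence. The exact set is a judgement, and smoking, also collected, could be argued for. What matters is that the set is fixed, with reasons, before the adherence data are examined.

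The cost is a change of SAP wording and about two degrees of freedom out of some 296. No new data are needed, and the primary estimate stays as it is.

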C.3.7 Data management. Data management and quality assurance will be jointly led by the UCSF and the BU Data Coordinating Center (DCC). As in the previous studies, tracking information will be entered into a database which will generate reminders for follow-up visits. The tracking database will also be used to automatically randomize patients to study arms. The questionnaire data, brief assessments, laboratory results, and the CRF data will be entered directly into a laptop computer in Uganda while offline, and later uploaded to a secure server at UCSF. The EMM adherence data will be uploaded weekly to a secure website, cleaned, and merged with the other study data. All data will undergo weekly checks for completeness and range criteria.

C.3.8 Measurements.

Safety and tolerability. Safety will be assessed by the occurrence of a Grade 3/4 hepatotoxicity at any time during the assigned treatment period. Lack of tolerability will be defined as any treatment discontinuation prior to completion of the prescribed course due to side effects or ALT/AST elevations.

Adherence. We will measure medication adherence using EMM, pharmacy pill count, self-report, and INH concentration in hair. While there is no gold standard for determining medication adherence, EMM adherence has been highly predictive of undetectable HIV viral load¹¹²⁻¹¹⁴ is considered the reference standard,^{62,112,115,116} and therefore will be our primary measure of adherence. EMM adherence will be defined as the number of pill bottle openings (no more than 1 per day counted)¹¹³ divided by the number of prescribed doses over the study period. Adherence to vitamin B-6, which will be provided in a separate bottle, will not be part of the adherence measurement.

Self-reported adherence measures will include the visual analog scale (VAS) which asks the patient to identify their past month percent adherence on a visual scale that ranges from 0 to 100%, and the Self Rating Single Item (SRSI) adherence scale,^{117,118} which asks participants to rate their ability to take their medications as prescribed over the past month.¹¹⁹ Both of these measures are brief¹¹⁸ and are strong predictors of viral suppression.¹¹⁸ Lastly, we will collect hair samples at 3 months and 6 months, and will measure the INH concentration (ng/mg) in the hair.

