Secondary analyses: INH concentration in hair by drinking level. We will examine the level of INH drug concentration at 3 months and at the end of treatment overall among drinkers and by drinking level (3 groups). The analysis of this continuous measure will be as described for adherence, i.e. mean INH drug concentration will be estimated along with 95% CIs and the groups will be compared using multiple regression models.

C.3.11 Exploratory Aim 1 and Aim 2 analyses: predictors of toxicity and adherence. We will also perform analyses to identify potential predictors of hepatotoxicity and/or treatment discontinuation (grouped together to increase statistical power) and adherence measures. Several potential predictors will be considered including demographics, body mass index, time updated heavy alcohol use, ART adherence, baseline HbSag, measures of cirrhosis (Fib-4 score and/or platelet count), and kidney function (eGFR). Given the limited number of events compared to predictors of interest, we will build a regression model using the lasso (least absolute shrinkage and selection operator) method, a variable selection approach that fits a regression model including all independent variables and covariates of interest but constrains some coefficient estimates by shrinking them to zero to reduce variance.^{130,131}

C.3.13 Missing data. We will evaluate differences in baseline characteristics between those lost to follow-up versus those who are retained to examine missing data mechanisms, e.g., missing completely at random (MCAR), missing at random (MAR), or missing not at random (MNAR).¹³² If it is reasonable to assume that data are MAR, multiple model based imputation methods will be applied to account for the missing data.^{132,133}

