Adherence and treatment default. In each month while taking TB preventive therapy, simulated individuals have a probability of non-adherence and/or treatment default, i.e. treatment discontinuation that is unrelated to hepatotoxicity. Simulated patients who stop medications do not accrue the full benefit of prevention, though incomplete courses of therapy confer partial preventive benefits.²¹ One challenge to incorporating treatment adherence data in a decision analytic model is that the effectiveness of various levels of adherence to TB preventive therapy is not known. We will therefore model discontinuation/default and low adherence in two ways: First, we will use WHO definitions of treatment loss to follow-up for active tuberculosis treatment to model TB preventive therapy adherence as a binary outcome (yes/no).⁹ We will define "not adherent" as any patient who misses two consecutive monthly refill visits, or who, for 2 consecutive months, self-reports taking <80% of his/her intended doses of therapy, or whose EMM cap data indicates <80% of doses taken. In the simulation model, individuals will not accrue any benefits (or risks) of therapy after the month that the patient is classified as "non-adherent." Second, we will use EMM adherence data to model non-adherence as a continuous outcome. We will assume that taking fewer than the total number of TB preventive therapy doses throughout the entire course of therapy has the same effect as taking 100% of doses for fewer months than recommended. For example, we will assume that taking 50% of doses for six months of therapy provides similar treatment efficacy as taking 100% of all doses for only 3 months. We will compare the results of these two strategies and thus gain information on the relative importance of how adherence is modeled.

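### No rule says how adherence is scored after default or loss to follow-up, and the general MAR imputation rule may overstate mean adherence in Aim 2

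*Combined protocol and SAP*

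**What the plan says.** All references are to the combined protocol and SAP.

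- **Outcome (C.3.8, Adherence).** Primary adherence is EMM bottle openings, at most one per day, "divided by the number of prescribed doses over the study period".
- **Analysis set (C.3.10).** "The analysis will consist of all participants enrolled".
- **Stopping rule (C.3.10).** "For those who are advised to discontinue therapy by the study physicians, adherence up until discontinuation will be used". The sensitivity analyses attached to this rule include "assuming the worst case scenario of zero for the discontinued time period". Participants who stop on their own decision, or who stop attending, are not mentioned.
- **Missing data (C.3.13).** "We will evaluate differences in baseline characteristics between those lost to follow-up versus those who are retained to examine missing data mechanisms". Then: "If it is reasonable to assume that data are MAR, multiple model based imputation methods will be applied to account for the missing data". No outcome is named, and no method is given for the case where MAR is rejected.
- **Supply and data (Table 3).** Refill, pill count and EMM download share the same visits, at week 2 and months 1 to 6.
- **Aim 3 (C.4.2, Adherence and treatment default).** In the binary version of the decision model, the non-adherent category includes "any patient who misses two consecutive monthly refill visits".

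**The concern.** Two things go wrong together.

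First, the check cannot do its job. A baseline difference between lost and retained participants is evidence against MCAR. Whether the data are MAR or MNAR depends on the unseen adherence values given what was observed, and baseline variables do not carry that information.

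Second, much of what would be imputed is not missing. A participant who stops attending receives no further scheduled refill. After the last dispensed pills are used up, the number of study doses taken is zero by design. MAR imputation would give those days the adherence of similar people who kept refilling. The monthly linear mixed model in C.3.10 does much the same if those months are simply absent, because it then relies on MAR implicitly.

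At stake is the main Aim 2 result, mean adherence among drinkers. The same data feed Aim 3, where the second modelling approach uses continuous EMM adherence. There is also a clash between aims: the same missed months could count as non-adherent in Aim 3 and carry imputed adherence in Aim 2.

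**Working it through.** **The plan's own figure.** C.3.9 expects 90% retention at the 6-month visit: 200 × 0.90 = 180 evaluable drinkers, so 20 of 200 (10%) lost. This reproduces. The plan gives no expected adherence, standard deviation or sample size for Aim 2.

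**Inputs**
- From the documents: loss d = 10% (C.3.9); course length 6 months (C.3.5).
- Assumed: adherence while supplied, A = 70-95%; time of loss; supply left at loss of 0 or 1 month (the amount dispensed per visit is not stated); imputed adherence equal to A.

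**Formula.** Let f be the average share of the 6 months left uncovered among those lost.
- Mean under MAR imputation = A
- Mean with zeros after supply ends = (1 − d) × A + d × A × (1 − f)
- Overstatement = d × A × f

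**Loss spread evenly over 6 months**
- No supply left: f = 0.50.
- One month left: f = (5² / 2) / 6² = 12.5 / 36 = 0.347.

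| A | f = 0.50 | f = 0.347 |
|---|---|---|
| 70% | 3.5 points | 2.4 points |
| 80% | 4.0 | 2.8 |
| 90% | 4.5 | 3.1 |
| 95% | 4.8 | 3.3 |

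At A = 80% the zero-scored mean is 76.0% or 77.2%, against 80% under MAR.

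**Cross-check on the visit schedule.** Suppose the last attended visit is spread evenly over baseline, week 2 and months 1 to 5, and pills last exactly to the next visit. The uncovered months are 5.5, 5, 4, 3, 2, 1 and 0, with mean 20.5 / 7 = 2.93. Then 0.10 × 0.80 × 2.93 / 6 = 3.9 points, and with A = 90%, 4.4 points.

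**Extremes at 10% loss**
- All lost at week 2, nothing left, A = 95%: 0.10 × 0.95 × 5.5 / 6 = 8.7 points.
- All lost at month 5 with one month left: 0 points.

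**Scale.** With n = 200 and a standard deviation of 20-30 points (assumed), the 95% CI half-width is 1.96 × 20 / √200 = 2.8 to 1.96 × 30 / √200 = 4.2 points. The bias could be as large as the reported uncertainty.

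**Contrast by drinking, illustration only.** C.2 cites an adjusted hazard ratio of 2.1 for discontinuing MDR-TB treatment with recent alcohol use. If that applied here with 10% loss in drinkers, loss in non-drinkers would be 1 − 0.90^(1/2.1) = 4.9%. At A = 80% in both groups, the overstatement is 4.0 v 2.0 points (f = 0.50) or 2.8 v 1.4 points (f = 0.347). The difference between groups would shrink by about 1.4-2.0 points.

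**The case against.** The strongest reply is that the plan does not order the biased choice. C.3.13 is a general, conditional sentence that names neither adherence nor Aim 2. Read literally, the C.3.8 definition applied to everyone enrolled already gives zeros: a lost participant keeps the full denominator, and days without openings add nothing to the numerator. That reading is available, and it is the one the fix adopts. But C.3.13 sits among the methods for Aims 1 and 2, is the only text addressed to loss to follow-up, and points the other way. The analyst is left to choose.

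A second reply is that lack of drug is inferred. INH comes from the pharmacy that also supplies ART (C.3.5), and retention efforts include clinic alerts and home visits (C.3.6), so a missed study visit does not prove a missed refill. This stands. It is why the rule should run from the dispensing record and not from the visit record.

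Third, an imputation model that uses a participant's earlier EMM months could impute less than retained participants achieve. That would reduce the bias, but any imputed value above zero on a day without pills still overstates adherence.

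Fourth, Aim 3 is only partly exposed. Its binary approach already handles missed refills, and C.4.5 lists imperfect adherence among the candidates for probabilistic sensitivity analysis. This stands too.

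**Conclusion.** The point holds as a gap with a likely direction, not as a certain bias. The plan lets a check that cannot identify the mechanism open the way to MAR imputation of days without drug supply, and the zero-value analysis does not reach these participants. If that route is taken, mean adherence among drinkers is overstated by about 2.4-4.8 points at 10% loss, assuming even timing of loss, 70-95% adherence while supplied and zero to one month of pills left. Other timings give 0 to 8.7 points.

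A reader might infer three stronger things that the documents do not support:

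- **That post-loss adherence will be imputed.** Imputation is conditional and not tied to this outcome.
- **That the bias is largest in drinkers.** The 90% retention in the progress report is for the cohorts as a whole, with no split by drinking. The hazard ratio of 2.1 comes from MDR-TB treatment in another country. With equal loss and equal adherence while supplied, the bias is equal. Large contrasts also strain the plan's own numbers: C.3.9 expects heavy and moderate drinkers in about equal numbers, so 20% loss in heavy drinkers fits 10% overall only if moderate drinkers lose nobody (0.5 × 20% + 0.5 × 0% = 10%).
- **That the plan claims a baseline comparison can identify MNAR.** It says only that mechanisms will be examined.

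**What to change.** Amend C.3.10 and C.3.13 as follows.

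1. For participants who default or are lost, score every day after the last dispensed supply ends, by pharmacy dispensing record, as zero in the primary EMM measure and in the monthly mixed model. End the scoring period at death or documented transfer of care.
2. Restrict multiple imputation to days with pills in hand but no readable EMM data, and add a zero-adherence sensitivity analysis for those days.
3. Show MAR imputation of post-loss days only as a sensitivity analysis.
4. Keep the baseline comparison as description, and do not let it decide between MAR and MNAR.
5. Align the Aim 2 rule with the missed-refill definition in C.4.2, so that the same months are not treated in opposite ways.

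The cost is SAP wording and use of the dispensing records. The one downside is that reported adherence becomes slightly less favourable.
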